## **Secondary Outcome Measures:**

1. Agreement/disagreement of hospital staff regarding technology acceptance and adaptation

A survey was conducted using a self-structured questionnaire to get feedback from the hospital staff regarding their acceptance of the technology. The questionnaire contained questions regarding the physical (smell, appearance and feel) aspects of the coating as well as general approval/disapproval based on their experience with the technology. A scale of -5(worst) to +5(best), with 0 representing neutral was used, representing a dimensionless quantity based on staff's personal preferences. Mean of the user's response to each question was used for quantification. The users observed the technology during the entire 12 weeks of the study period (during all 3 phases of data collection). Users were give a 4-week time period to submit their survey responses.

[Time Frame: 4weeks]

[figure not shown]
Arms	Assigned Interventions

Active Comparator: Regular Patient privacy curtain
 
Control arm is a regular patient privacy curtain, washed and dried in hospital laundry using commercially available sodium hypochlorite and hydrogen peroxide.
	
Combination Product: Regular Patient privacy curtain
 
Laundered curtains, used in the hospital, coming from the hospital inventory.

Experimental Comparator: Antimicrobial Coated Curtains
 
Treatment arm is antimicrobial coated curtains that are coated by dipping method, dried and provided to nursing/supporting staff to change after every 3-4 weeks.
	
Combination Product: Regular patient privacy curtains
 
Antimicrobial Coated curtains

**Protocol:**

**1. Curtain receiving, coating, coding, and transportation:**

1. Every 2nd week, HKUST team received 26 washed (routinely cleaned) curtains from rehabilitation ward linen room on ground floor.
2. 13 curtains were kept in a designated cabinet in the linen room at 3rd floor Rehabilitation ward 3B. These 13 curtains were coded according to assigned numbers as control curtains.
3. 13 remaining washed curtains out of 26 were transported to HKUST by using three large luggage bags
4. As each curtain absorbs approx. 3 Liters of the coating solution, so our team had ensured availability of 30 liters of C16 coating material on completion of each phase.
5. Our team preferably prepared fresh C6 coating and diluted C6 in tap water at the time of coating to prepare C16.
6. We had three 95 Liters capacity big containers, that were used to coat the curtains in HKUST premises during Pilot study.
7. The best practice to coat the curtain was dipping method (dip a dry curtain in a filled container of C16 coating).
8. Curtains were soaked/dipped for 30 minutes in coating material to absorb properly and uniformly.
9. After soaking, curtains were squeezed gently to remove extra solution/liquid and transferred to clean and dry container.
10. 13 wet coated curtains were transferred to laundry to dry as following:
  - a. Hot air of 65°C for 30 minutes.

- b. Cold air of 20°C for 3-5 minutes to reduce the temperature of curtains.
11. 13 dry, coated curtains were brought back to the linen room of rehabilitation ward, coding was done according to the assigned number to keep the study blind. Only principal investigator has the knowledge of the factitious codes to keep study double blind.
12. All the curtains (13 coated and 13 uncoated) were prepared for installation in 1 week including receiving, transportation, coating, drying, and coding during pilot study.
13. Drying protocol amendment
- Drying protocol was amended due to shedding of coating in heavy circular mechanical motion in laundry dryer. For this purpose, curtains were kept on room temperature for overnight, and next morning when there was no apparent dipping, they were shifted to walk in incubator of Pathology lab at 50°C for 24-36 hours for best drying results.
  - Drying in HKUST premises was difficult with minimum resources, heavy weight and humidity issue along with transportation.

\*1 extra pair of curtains for control and treatment end was kept as a back up

Fig 1. Illustration of coating in container, method of coating by dipping method, squeezing, transportation and drying of patient privacy curtains

## 2. Curtain installation:

1. Every 3rd week, our team changed the curtains from 2 cubicles (1 male and one female) according to curtain changing policy of hospital.
2. At the start of every phase of study, following the standard protocol; after taking official consent from ward manager we changed the curtains at once from both cubicles.
3. There were two types of curtains clippings, with metal ring and cloth strips so that curtains were changed according to the type of clips/ring.
4. As there was the capacity of 12 curtains in one cubicle, so six curtains were coated and six uncoated. The sequence was alternative as one coated next uncoated and so on. After installation, we informed ward manager about completion of curtain hanging in the designated ward and took first sample at day 7 because we gave sufficient time to curtains to be contaminate in hospital environment.
5. There was a backup pair of the curtain in case of need to change curtain due to spoilage, vomitus, blood or MDRO diagnosed the patient. Staff was informed to notify our team about the date and reason of curtain changing.

[figure not shown]

Fig 2. Illustration of curtains installation in cubicles as one control other treatment showing matched paired randomization

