### Sampling Duration, Time Frame, and work plan:

Background /Pilot Study	Survey	Observation Period (1 st Data Set/Phase 1 )	Washo ut	Survey	Observation Period (2 nd Data Set/ Phase 2)	Wash out	Survey	Observation Period (3 rd Data Set/ Phase 3)
8 weeks	4 weeks	4 weeks	3 week	2 Week	4 weeks	3 week	2 week	4 weeks
04 Sep -30 Oct (2017)	31 Oct – 28 Nov (2017)	01 Dec - 30 Dec (2017)	1st Jan - 05 Feb (2018)		06 Feb – 08 Mar (2018)	26 Mar – 30 Apr (2018)		22 May – 20 Jun (2018)
		8 curtains from Male  12 curtains from Female Cubicle  50% coated curtain, 50% standard curtain			12 Curtains from Male Cubicles  12 Curtains from Female Cubicle  50% coated curtain, 50% standard curtain			16 Curtains from Male Cubicles  16 Curtains from Female Cubicle  50% coated curtain, 50% standard curtain
		No of samples: 480			No of samples: 576			No of samples: 768

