## **Detailed Description:**

[1] A multi-level antimicrobial coating was produced in the HKUST laboratory using the newly developed staged flow micromixing to prepare contact-killing and anti-adhesion coating made of US-FDA approved polymeric materials. The process was optimized to scale-up the production to 5 liters per hour. 300 liters of the multi-level antimicrobial coating was prepared for the study for a total of 24 weeks as three liters of the coating was needed for one patient privacy curtain.

[2] The study was conducted in the rehabilitation ward of the Kowloon Hospital including both male and female cubicles. It was carried out in three stages with each stage consisting of survey and a four weeks' observation period, separated by three weeks' washout period. In the rehabilitation ward of Kowloon Hospital, a set of male and female cubicle was recruited for the study after getting maximum number of bacterial contamination on patient privacy curtains in pilot study of 8 weeks. Each cubicle had 12 curtains besides admitted patients where all the samples are collected.

[3] Environmental sampling was carried out using sponge swab on the surfaces of the patient privacy curtains. The total bacteria count and quantitative isolation of MRSA was done using established protocols. The total bacteria count provides a quantitative measure of surface cleanliness, while the MRSA count was indicative of the risk of contact transmission from contaminated surfaces. 2-4 weeks survey provided control data on the cleanliness of patients privacy curtains in terms of total bacteria and MRSA counts.

During the study period, the Kowloon Hospital/Queen Elizabeth Hospital infection control team monitored MDROs regularly as part of their routine operation. The procedure and schedule was followed strictly the infection control protocol. All infection control measures implemented after isolation of MDROs were followed according to the hospital's usual practice as advised by the infection control team. In the study, the identification of the organisms in patients more than 48 hours after admission without prior isolation of the organisms in clinical or screening specimens was defined as nosocomial.

[4] The investigators demonstrated a cross-over intervention study. In the first stage of study, half of the patient privacy curtains were considered as treatment (antimicrobial coated) and the other

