half of the curtains as control in the same setting in a cubicle. As the study was double blind, so coding was done to identify the treatment as control curtains.

[5] Sample were taken from eight highly touched areas of 50x50 cm^2 on weekly bases for three consecutive weeks on 7th day of first installation. On each period/phase 480, 576 and 786 samples were collected accordingly using the developed sample protocol. In total, the investigators collected 1824 samples from 76 patient privacy curtains in which 912 (50%) were control curtain and 912 (50%) are antimicrobial coated curtains.

[6] Healthcare workers from the participating wards were assessed for their acceptance of the multilevel antimicrobial disinfectant coating by way of a questionnaire. Additional reformulation may be necessary to increase the acceptability of the coating technology to the healthcare workers.

[7] For the bacteria count, duplicate plates of TSA (total bacteria count) and Chromagar MRSA (selective agar for MRSA detection) were used for enumeration. CFU/m^2 is calculated after 48 hours' incubation at 37C. Data was analyzed using SPSS V.21 to assess the effectiveness of the coating in reducing the contamination level of the surface. The total bacteria count on the patient privacy curtains was compared between the control and treatment group using Mann-Whitney test and T-test. ANOVA analysis allowed the comparison of different periods of study of phase wise as well as week wise. The significance of the statistical test is defined to have a P value <0.05.

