#### 3. Pouring of neutralizer into sponge containing zip bags:

- 10ml of neutralizing solution was poured into sterilized empty zip plastic bags.
- We used a new 10ml pipette glass tube and electric pipette to pour neutralizer on

operation bench in KH core lab, before sampling.

c. The team dealing with neutralizer pouring was operating carefully to measure the appropriate amount, prevent spoilage and maintain hygiene and safety.

d. Zipped bags were opened minimally, to reduce the chances of contamination.

4. Labelling:

a. All the bags were labelled before sampling

b. Labelled the bags with bed number, coding, sampling area

5. Transportation Containers:

a. Sampling material containers were have following items to bring in rehabilitation ward (1 set for male and similar another set for female cubicle) for 1-time sampling:

- Polywipe sponges 110, (required 96, extra 14 in case of contamination/ fall in floor during sampling)
- Plastic gloves (blue colored), already given in polywipe sponge box
- Plastic holding clips, to identify measured area
- Measuring tapes, to measure 50x50cm^2 area as a sampling area
- Neutralizing solution in zipped labelled bags 110, (required 96, extra 14 in case of contamination/ fall in floor/ leakage)
- Autoclave medium size bag to put used gloves used sponge and wrappers of sponge

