## **Sampling Arrangements and methods:**

1. Sampling Cubicles (Location): one male cubicle (3rd cubicle) and one female cubicle were allocated for this study after pilot study results. These were located on 3rd floor or rehabilitation building (ward 3B).

2. Sampling time: Every visit, sampling was started at 8:30 am and finished till 12:00 pm.

3. Following the Rules: Sampling team had to follow the rules of Kowloon Hospital in rehab wards. The team had to sample curtains smoothly and quietly to minimize disturbance to working staff as well as patients in beds. The team was not allowed to encroach patient treatment or investigations/ file to keep the confidentiality.

4. Gowning for safety: All the members were gowned properly by wearing personal protective equipment (disposable gown, gloves, mask and head cover). For gowning, individual followed the step mentioned in safety training, as all sampling taking persons had gone through safety training by infection control team of Kowloon Hospital.

5. Sample taking notification and Consent: Team was notifying ward manager/ ward in-charge about sampling plan and take verbal permission to proceed.

6. Sampling Teams: In the female cubicle, two female team members took samples. One

member was take a sample of swabbing the area; other was helping to provide gloves, sponge, identification of appropriate area, calibrate the size and provide support by holding the frame of 50x50cm^2. The same sampling protocol was adopted in a male cubicle where male team members were taking the samples.

7. Safety precaution:

Following safety measures were accomplished before and during sampling:

- a. Before sampling, clean the hands having gloves with available disinfectant.
- b. Put plastic disposable gloves and take out sponge from its plastic packing.
- c. Again disinfect plastic gloves and let it dry for few second.
- d. Hold the sponge firmly from one side and keep sampling designed 50x50cm^2 area.
- e. Don't touch any other, other area holding the sponge, and prevent felling down on contaminated floor
- f. In case, sponge was touch with other surface or fell on floor, please discard that sponge and resample the same area with a new sponge

8. Sample preservation:

- a. After proper sampling, we put the sponge in zipped plastic bag containing 10 ml neutralizing solution quickly to reduce chance of contamination

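### The 32 curtains counted in phase 3 do not fit the two 12-curtain cubicles described, so the source of at least 8 curtains (192 samples) is unexplained and the phase-wise ANOVA may confound phase with cubicle

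*Combined protocol and SAP*

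**What the plan says.** Five places in the combined protocol and SAP describe, or fit, two cubicles of 12 curtains:

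- Sampling Arrangements and methods, item 1: "one male cubicle (3rd cubicle) and one female cubicle were allocated for this study after pilot study results".
- Curtain installation, item 1: "our team changed the curtains from 2 cubicles (1 male and one female". Item 4 of that section: "As there was the capacity of 12 curtains in one cubicle, so six curtains were coated and six uncoated".
- Detailed Description, paragraph 2: "Each cubicle had 12 curtains besides admitted patients where all the samples are collected".
- Transportation Containers, supplies for one cubicle at one visit: "Polywipe sponges 110, (required 96, extra 14 in case of contamination/ fall in floor during sampling".
- Curtain receiving, coating, coding, and transportation: "All the curtains (13 coated and 13 uncoated) were prepared for installation in 1 week". One curtain of each type is a spare, which leaves 24 to hang. That sentence goes on to refer to the pilot study, so it supports the count without settling it.

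The work plan table (Sampling Duration, Time Frame, and work plan) counts differently. It lists 8 male and 12 female curtains in phase 1, 12 and 12 in phase 2, and for phase 3 "16 Curtains from Male Cubicles" with the same number from the female side. Its sample counts are 480, 576 and 768. Paragraph 5 of the Detailed Description reports 76 curtains and 1824 samples in total.

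On analysis, paragraph 7 of the Detailed Description states: "ANOVA analysis allowed the comparison of different periods of study of phase wise as well as week wise". The Data Analysis section repeats the comparison of periods. Neither gives a model containing both phase and cubicle.

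**The concern.** One cubicle with room for 12 curtains cannot hold the 16 that the work plan assigns to each sex in phase 3. No section says where the others hung.

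Two things depend on the answer. The first is the record of what was sampled: the reported totals are correct only if the two-cubicle description is not. The second is the phase comparison. The study cubicles were chosen after the pilot because their curtains showed the heaviest contamination. A cubicle brought in for phase 3 would lie outside that documented selection and could have a different baseline. An ANOVA with phase and no cubicle term would attribute that difference to phase.

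**Working it through.** **Inputs.** Areas per curtain: 8, and samplings per curtain: 3 (both Environmental Sampling). Capacity per cubicle: 12, and cubicles: 2 (Curtain installation; Sampling Arrangements). Curtains per phase: 20, 24 and 32 (work plan table). Swabs per curtain: 8 × 3 = 24.

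**1. The plan's own totals.**
- Phase 1: (8 + 12) × 24 = 480
- Phase 2: (12 + 12) × 24 = 576
- Phase 3: (16 + 16) × 24 = 768
- Total: 76 curtains, 76 × 24 = 1824

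These reproduce the work plan and the reported total. The Detailed Description gives 786 for phase 3, and 480 + 576 + 786 = 1842. That looks like a transposition of 768 and should be corrected in the same pass.

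**2. What the described layout can hold.**
- Per phase: 2 × 12 = 24 curtains, 24 × 24 = 576 samples
- Ceiling over three phases: 3 × 576 = 1728 (72 curtains)
- With phase 1 at its listed 20 curtains: (20 + 24 + 24) × 24 = 1632 (68 curtains)
- Phase 3 excess: 32 − 24 = 8 curtains (25% of 32), and 768 − 576 = 192 samples

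**3. Supplies.** Sponges needed per cubicle: 12 × 8 = 96, as the plan says. Sixteen curtains would need 16 × 8 = 128, more than even the 110 packed with spares. Phase 3 would also need 16 coated curtains, against 13 described per batch.

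**4. Could replacements explain it?** No, for three reasons.
- Only one back-up pair is described, so at most 24 + 2 = 26 curtains.
- A replacement takes over a position already counted. Twenty-four positions × 8 areas × 3 weekly samplings remain 576 however many curtains are exchanged.
- A count of 768 requires all 32 curtains to be sampled three times. With a first sample on day 7 and weekly samples after that, a curtain needs about 21 days on the rail. Two in succession on one rail need about 42; phase 3 ran from 22 May to 20 June, 30 days.

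**5. Could it be a fourth sampling?** 24 × 8 × 4 is also 768. But that contradicts the three samplings per curtain, the 16 + 16 in the work plan and the 76 curtains reported.

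**6. Effect on the sample size.** The plan's minimum reproduces: one-sided α = 0.05, power 0.95, d = 0.20 give n per group = 2 × (1.645 + 1.645)² / 0.20² ≈ 541.2, rounded up to 542, total 1084. On the plan's own basis, which treats swabs as independent, power is Φ(0.20 × √(N/4) − 1.645): 0.992 at 1632, 0.994 at 1728 and 0.996 at 1824.

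**7. Sex mix.** The male share is 8/20 = 40% in phase 1 and 50% in phases 2 and 3.

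**The case against.** The strongest reply is that this is a documentation slip with little statistical consequence. Much of that stands.

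- **Sample size.** A reader might infer that the study falls short because 1728 is below 1800. The documents do not support that: 1084 is the calculated requirement, and 1800 was chosen to suit ward size and schedule.
- **Arm comparison.** A reader might infer bias between coated and standard curtains. Every phase is listed as half coated and half standard, with the two types alternating within a cubicle. If extra cubicles were hung the same way, the arms stay balanced within each. Alternation is described only for the two named cubicles, so this cannot be confirmed for the additional curtains, but bias is not shown.
- **Mixed cubicles.** A reader might take it as established that the phases used different cubicles. The counts for phases 1 and 2 fit the same two; only phase 3 is in doubt, and no section says which cubicles supplied it. The plural in the phase 3 entry is weak evidence, because the phase 2 entry uses it too with only 12 curtains.
- **Replacements.** Curtains could be changed after soiling or an MDRO diagnosis, so a reader might suspect an outcome-related source for the extra eight. The stated back-up stock and sampling schedule rule that out.
- **Scope.** The phase-wise ANOVA is not a listed outcome. The comparison of arms and the durability outcome within each phase do not rest on comparing phases.

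What the reply does not remove is the contradiction itself, or the fact that the planned phase comparison cannot be interpreted until it is resolved. The Data Analysis section mentions differences among wards, but the study sits in one ward and no adjustment for cubicle is stated.

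**Conclusion.** The contradiction is real and nothing in the documents resolves it. Phase 3 exceeds the described capacity by 8 curtains and 192 samples, and the reported 76 curtains and 1824 samples depend on that excess. The described layout supports at most 1728 samples, or 1632 using the listed phase 1 count. This assumes that 12 is the true capacity, that two cubicles were used, and that each curtain was sampled three times at eight areas. If the third holds, one of the first two must be wrong for phase 3.

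The consequence is limited. Power on the plan's own basis stays at about 0.99, and no bias between arms is demonstrated. The phase-wise ANOVA is exposed only if cubicles were added in phase 3, which is a reasonable inference but not a documented fact. Separately, the lower male share in phase 1 is a smaller imbalance between phases that the ANOVA as stated does not address. The size of any cubicle effect cannot be estimated from the documents.

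**What to change.** - **Reconcile the text.** From the curtain log, state for each phase which cubicles were used, how many curtains of each type hung in each, and any replacements. Bring the work plan table, Detailed Description (including the 786), Curtain receiving, Curtain installation, Transportation Containers and Sampling Arrangements into agreement, and correct the curtain and sample totals if the log requires it.
- **Phase comparison.** Fit the phase ANOVA with cubicle as a factor, or restrict it to cubicles present in all three phases. Because the two named cubicles are one male and one female, either choice also deals with the different sex mix in phase 1. Both need some cubicles to be common to the phases; if the log shows none, phase and cubicle cannot be separated and the report should say so.
- **Arm comparison.** Include cubicle as a blocking factor, since coated and standard curtains were alternated within it. This is for precision and to match the design, not to correct a demonstrated bias.

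The cost is a check of existing records and one added factor. A phase comparison restricted to common cubicles may use fewer curtains. No new data are needed, which matters because collection is complete.

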## **Study Design:**

Interventional cross-over study

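### The only allocation rule described is alternation, which does not support the randomisation and cross-over labels and leaves the arm contrast open to an every-second-position effect

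*Combined protocol and SAP*

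**What the plan says.** All references are to the combined protocol and SAP.

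- **Allocation rule** (2. Curtain installation, item 4): "As there was the capacity of 12 curtains in one cubicle, so six curtains were coated and six uncoated", followed by "The sequence was alternative as one coated next uncoated and so on". Item 3 of the same section adds that the curtain hung also had to match one of two clip types.
- **Randomisation label** (Fig 2 caption, same section): "Illustration of curtains installation in cubicles as one control other treatment showing matched paired randomization". This is the only use of the word in the available text, and the figure itself is not shown.
- **Cross-over label** (Study Design): "Interventional cross-over study". The Detailed Description, paragraph 4, repeats it: "The investigators demonstrated a cross-over intervention study". The only allocation described after that is an even split for the first stage, with both arms side by side: "half of the curtains as control in the same setting in a cubicle".
- **Phases** (Sampling Duration, Time Frame, and work plan): each of the three phases is listed as "50% coated curtain, 50% standard curtain", with washouts between phases and no rule for exchanging arms.
- **Choice of curtains to coat** (Protocol, section 1): of 26 laundered curtains, 13 are set aside as controls and the other 13 are coated. How the two sets are chosen is not described. The codes are described as serving the blind.
- **Analysis**: the sample size is for two independent means. Data Analysis compares the arms by Mann-Whitney test and t test, and uses ANOVA to compare periods and wards.

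**The concern.** Systematic alternation, randomisation within matched pairs, and a cross-over are three different designs, and they license different inferences. With randomisation within pairs, position effects average out over the draw. In a cross-over, each unit (a curtain or a bed position) receives both conditions, so stable differences between units cancel. Alternation alone does neither. It fixes which positions share an arm once the starting arm is chosen.

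If contamination differs systematically between odd and even positions, and the starting arm was the same throughout, that difference becomes part of the estimated coating effect. One way this could arise is two curtains per bed with one side touched more often, but the documents do not say how many curtains serve a bed. The planning effect is small, so even a modest position effect would matter. A reader who takes either label at face value would also credit the data with protection that the described procedure does not provide.

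**Working it through.** **1. The plan's own figure.** Inputs from the sample size section: d = 0.20, SD 1 log, one-sided alpha 0.05, power 0.95. The normal approximation gives n = 2 × (1.645 + 1.645)² / 0.20² = 541.1, so 542 per group. The exact noncentral t calculation also gives 542 per group, 1084 in total, with power 0.950067, as stated. The calculation uses two independent groups, with no pairing and no cross-over. Nothing in this point changes that number.

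**2. Does any unit receive both conditions?** Curtains by phase are 8 + 12 = 20, 12 + 12 = 24 and 16 + 16 = 32. The total is 76, and 76 × 8 areas × 3 weeks = 1824 samples, 912 per arm. Since 912 / 24 = 38, the plan's count is 38 coated and 38 control curtains: each curtain is counted once, in one arm. As for positions, phase 3 has four more male and four more female curtains than phase 2, so at least 8 phase 3 curtains hung at positions not sampled in phase 2. Sixteen curtains also exceed the stated capacity of 12 per cubicle, so the six-and-six rule does not by itself describe phase 3.

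**3. How many layouts does the rule allow?** For one cubicle of 12:
- alternation: 2 layouts, or 1 if the starting arm is fixed
- random choice within 6 adjacent pairs: 2⁶ = 64
- free 6/6 randomisation: 924

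**4. Smooth gradient.** Suppose contamination changes by g log per position. Odd positions (1, 3, …, 11) average 6 and even positions (2, 4, …, 12) average 7, so the bias is one step, g, against a range of 11g across the cubicle. Alternation therefore leaves 1/11, about 9%, of the range.

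**5. Odd/even effect.** Let odd and even positions differ by p log. The documents give no value; p = 0.05 to 0.10 is an assumption. With a constant starting arm the bias is p in full:
- 0.05 / 0.20 = 25%
- 0.10 / 0.20 = 50%

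Against the 0.21 log named in the plan's assumptions these become 24% and 48%. Against the earlier study's difference, 4.32627 − 4.13126 = 0.195, they become 26% and 51%.

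**6. Effect on the test.** Take no coating effect, 912 samples per arm, SD 1 log, and samples treated as independent, as the plan does. The standard error is √(2/912) = 0.0468. An odd/even effect of 0.05 or 0.10 log would be declared significant in about 28% or 69% of trials one-sided, and 19% or 57% two-sided. Repeated samples from the same curtain are not independent, so these figures are illustrative only.

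**7. What would remove the bias?**
- *Reversing the start each phase, pooled contrast:* the remaining share is (20 − 24 + 32) / 76 = 28 / 76 = 37%, so 0.05 becomes 0.018 and 0.10 becomes 0.037.
- *Reversing with phase weights ¼, ½, ¼:* ¼ − ½ + ¼ = 0, if p is the same in every phase. The relative variance is (0.0625/20 + 0.25/24 + 0.0625/32) / (1/76) = 0.01549 / 0.01316 = 1.18, assuming equal variance per curtain.
- *Random draw in each of 76 / 2 = 38 pairs:* expected bias zero, with SD p/√38, which is 0.008 or 0.016 log.
- *Pair term with a constant start:* every within-pair difference still contains p, so the bias stays in full. A position term is then aliased with arm and cannot be estimated separately.

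**The case against.** The strongest reply is that the documents are silent on these matters rather than contradictory. The layout figure is not shown. The text does not say which arm started, or whether the start was the same in each cubicle and phase. The Detailed Description covers only the first stage, and washouts between phases fit a cross-over intention. A reader might infer that no randomisation or swap took place, or that one fixed order was repeated in all three phases. The documents support neither inference, and the changing curtain counts make an identical pattern in every phase an assumption.

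A reader might also infer that the arm comparison is in fact biased by door, sink or aisle effects. The documents do not support that either. They report no such effect, and alternation handles smooth trends well (step 4). Only a pattern with a period of two positions, combined with a constant start, gives the full bias, and its size here is assumed.

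All of that stands, and it limits the point to what is described. It does not rescue the labels. The stated rule is systematic, and no draw or exchange is described. Mann-Whitney is an unpaired test, the t test is not described as paired, and ANOVA compares periods rather than adjusting the arm contrast for pair or position.

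**Conclusion.** The point holds in this form: the described procedure is a concurrent comparison with alternating allocation, repeated in three phases, and it does not support the randomisation or cross-over labels. The planned arm tests do not use the pairing that the caption claims. The arms are balanced within cubicles, and smooth gradients are largely controlled. The remaining exposure is an odd/even position effect under a constant starting arm. Its size cannot be derived from the documents; at an assumed 0.05 to 0.10 log it would be 25% to 50% of the 0.20 log planning effect. The stated sample size reproduces and is unaffected. This should be corrected, because it changes what the design can claim, but it does not show that the result is wrong.

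**What to change.** **For the data already collected** (Study Status says completed):
- State how the starting arm and the curtains to be coated were chosen, and tabulate the arm at each bed position in each phase. Sample bags carried bed number and code, so this should be recoverable if those labels were transcribed.
- Unless a random draw or swap can be documented, replace both labels with: concurrent comparison with alternating allocation, repeated in three phases.
- Analyse the arm contrast by pair, cubicle and phase. Add a position term only if arms changed position between phases. If they did not, state as a limitation that position is aliased with arm.

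The cost is a table, a change of wording and a re-analysis, with no new samples.

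**For a repeat of the design:** within each adjacent pair of the same clip type, draw the coated position at random in each phase, and analyse within-pair differences stratified by cubicle and phase. If positions are exchanged between phases instead, weight the phases so that the exchange balances; with weights ¼, ½, ¼ and these phase sizes, that costs about 18% in variance. The random draw needs one coin toss per pair at hanging and no extra curtains.
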